	4.2.2 Age and sex				
	4.2.3 Country of origin	$\boxtimes$			9.2
	4.2.4 Disease/indication	$\boxtimes$			9.2
	4.2.5 Duration of follow-up			$\boxtimes$	
4.3	Does the protocol define how the study population will be sampled from the source population? (e.g. event or inclusion/exclusion criteria)	$\boxtimes$			9.2.2, 9.2.3
Comm	ents:				
Secti	on 5: Exposure definition and measurement	Yes	No	N/A	Section Number
5.1	Does the protocol describe how the study exposure is defined and measured? (e.g. operational details for defining and categorising exposure, measurement of dose and duration of drug exposure)			$\boxtimes$	
5.2	Does the protocol address the validity of the exposure measurement? (e.g. precision, accuracy, use of validation sub-study)			$\boxtimes$	
5.3	Is exposure categorised according to time windows?			$\boxtimes$	
5.4	Is intensity of exposure addressed? (e.g. dose, duration)			$\boxtimes$	
5.5	Is exposure categorised based on biological mechanism of action and taking into account the pharmacokinetics and pharmacodynamics of the drug?				
5.6	Is (are) (an) appropriate comparator(s) identified?			$\boxtimes$	

Template No.: RWI\_TP\_EPI0016 Revision 1 Reference: RWI\_WI\_EPI0005

European Medicines Agency Impact of EU label changes on methotrexate for weekly administration

Version 2.0 dated 21 February 2022

Reference: RWI\_WI\_EPI0005

Protocol/Study No: SC02 EMA/2018/19/PE Page 66 of 92

6.1 Does the protocol specify the primary and secondary (if applicable) outcome(s) to be investigated?  6.2 Does the protocol describe how the outcomes are defined and measured?  6.3 Does the protocol address the validity of outcome measurement? (e.g. precision, accuracy, sensitivity, specificity, positive predictive value, use of validation sub-study)  6.4 Does the protocol describe specific outcomes relevant for Health Technology Assessment? (e.g. HRQoL, QALYs, DALYS, health care services utilisation, burden of disease or treatment, compliance, disease management)  Comments:  Section 7: Bias  Yes No  7.1 Does the protocol address ways to measure confounding? (e.g. confounding by indication)  7.2 Does the protocol address selection bias? (e.g. healthy user/adherer bias)  7.3 Does the protocol address information bias? (e.g. misclassification of exposure and outcomes, time-related bias)  Comments:  Section 8: Effect measure modification  8.1 Does the protocol address effect modifiers? (e.g. collection of data on known effect modifiers, subgroup analyses, anticipated direction of effect)	N/A  N/A  N/A		Section Number
6.1 Does the protocol specify the primary and secondary (if applicable) outcome(s) to be investigated?  6.2 Does the protocol describe how the outcomes are defined and measured?  6.3 Does the protocol address the validity of outcome measurement? (e.g. precision, accuracy, sensitivity, specificity, positive predictive value, use of validation sub-study)  6.4 Does the protocol describe specific outcomes relevant for Health Technology Assessment? (e.g. HRQoL, QALYs, DALYS, health care services utilisation, burden of disease or treatment, compliance, disease management)  Comments:  Section 7: Bias  Yes No  7.1 Does the protocol address ways to measure confounding? (e.g. confounding by indication)  7.2 Does the protocol address selection bias? (e.g. healthy user/adherer bias)  7.3 Does the protocol address information bias? (e.g. misclassification of exposure and outcomes, time-related bias)  Comments:  Section 8: Effect measure modification  8.1 Does the protocol address effect modifiers? (e.g. collection of data on known effect modifiers, subgroup analyses, anticipated direction of effect)			Number
6.1 Does the protocol specify the primary and secondary (if applicable) outcome(s) to be investigated?  6.2 Does the protocol describe how the outcomes are defined and measured?  6.3 Does the protocol address the validity of outcome measurement? (e.g. precision, accuracy, sensitivity, specificity, positive predictive value, use of validation sub-study)  6.4 Does the protocol describe specific outcomes relevant for Health Technology Assessment? (e.g. HRQoL, QALYs, DALYS, health care services utilisation, burden of disease or treatment, compliance, disease management)  Comments:  Section 7: Bias  Yes No  7.1 Does the protocol address ways to measure confounding? (e.g. confounding by indication)  7.2 Does the protocol address selection bias? (e.g. healthy user/adherer bias)  7.3 Does the protocol address information bias? (e.g. misclassification of exposure and outcomes, time-related bias)  Comments:  Section 8: Effect measure modification  8.1 Does the protocol address effect modifiers? (e.g. collection of data on known effect modifiers, subgroup analyses, anticipated direction of effect)			Number
applicable) outcome(s) to be investigated?  6.2 Does the protocol describe how the outcomes are defined and measured?  6.3 Does the protocol address the validity of outcome measurement? (e.g. precision, accuracy, sensitivity, specificity, positive predictive value, use of validation sub-study)  6.4 Does the protocol describe specific outcomes relevant for Health Technology Assessment? (e.g. HRQoL, QALYs, DALYS, health care services utilisation, burden of disease or treatment, compliance, disease management)  Comments:  Section 7: Bias  7.1 Does the protocol address ways to measure confounding? (e.g. confounding by indication)  7.2 Does the protocol address selection bias? (e.g. healthy user/adherer bias)  7.3 Does the protocol address information bias? (e.g. misclassification of exposure and outcomes, time-related bias)  Comments:  Section 8: Effect measure modification  8.1 Does the protocol address effect modifiers? (e.g. collection of data on known effect modifiers, subgroup analyses, anticipated direction of effect)	N/A		0.2.2
and measured?  6.3 Does the protocol address the validity of outcome measurement? (e.g. precision, accuracy, sensitivity, specificity, positive predictive value, use of validation sub-study)  6.4 Does the protocol describe specific outcomes relevant for Health Technology Assessment? (e.g. HRQoL, QALYS, DALYS, health care services utilisation, burden of disease or treatment, compliance, disease management)  Comments:  Section 7: Bias  7.1 Does the protocol address ways to measure confounding? (e.g. confounding by indication)  7.2 Does the protocol address selection bias? (e.g. healthy user/adherer bias)  7.3 Does the protocol address information bias? (e.g. misclassification of exposure and outcomes, time-related bias)  Comments:  Section 8: Effect measure modification  8.1 Does the protocol address effect modifiers? (e.g. collection of data on known effect modifiers, subgroup analyses, anticipated direction of effect)	N/A		022
measurement? (e.g. precision, accuracy, sensitivity, specificity, positive predictive value, use of validation sub-study)  6.4 Does the protocol describe specific outcomes relevant for Health Technology Assessment? (e.g. HRQoL, QALYS, DALYS, health care services utilisation, burden of disease or treatment, compliance, disease management)  Comments:    Section 7: Bias	N/A	$\boxtimes$	9.3.2
Health Technology Assessment? (e.g. HRQoL, QALYs, DALYS, health care services utilisation, burden of disease or treatment, compliance, disease management)  Section 7: Bias  7.1 Does the protocol address ways to measure confounding? (e.g. confounding by indication)  7.2 Does the protocol address selection bias? (e.g. healthy user/adherer bias)  7.3 Does the protocol address information bias? (e.g. misclassification of exposure and outcomes, time-related bias)  Comments:  Section 8: Effect measure modification  8.1 Does the protocol address effect modifiers? (e.g. collection of data on known effect modifiers, subgroup analyses, anticipated direction of effect)	N/A		
Section 7: Bias  7.1 Does the protocol address ways to measure confounding? (e.g. confounding by indication)  7.2 Does the protocol address selection bias? (e.g. healthy user/adherer bias)  7.3 Does the protocol address information bias? (e.g. misclassification of exposure and outcomes, time-related bias)  Comments:  Section 8: Effect measure modification  8.1 Does the protocol address effect modifiers? (e.g. collection of data on known effect modifiers, subgroup analyses, anticipated direction of effect)			
7.1 Does the protocol address ways to measure confounding? (e.g. confounding by indication)  7.2 Does the protocol address selection bias? (e.g. healthy user/adherer bias)  7.3 Does the protocol address information bias? (e.g. misclassification of exposure and outcomes, time-related bias)  Comments:  Section 8: Effect measure modification  8.1 Does the protocol address effect modifiers? (e.g. collection of data on known effect modifiers, subgroup analyses, anticipated			
7.1 Does the protocol address ways to measure confounding? (e.g. confounding by indication)  7.2 Does the protocol address selection bias? (e.g. healthy user/adherer bias)  7.3 Does the protocol address information bias? (e.g. misclassification of exposure and outcomes, time-related bias)  Comments:  Section 8: Effect measure modification  8.1 Does the protocol address effect modifiers? (e.g. collection of data on known effect modifiers, subgroup analyses, anticipated direction of effect)			
(e.g. confounding by indication)  7.2 Does the protocol address selection bias? (e.g. healthy user/adherer bias)  7.3 Does the protocol address information bias? (e.g. misclassification of exposure and outcomes, time-related bias)  Comments:  Section 8: Effect measure modification  8.1 Does the protocol address effect modifiers? (e.g. collection of data on known effect modifiers, subgroup analyses, anticipated direction of effect)	$\square$	N/A	Section Number
User/adherer bias)  7.3 Does the protocol address information bias? (e.g. misclassification of exposure and outcomes, time-related bias)  Comments:  Section 8: Effect measure modification  8.1 Does the protocol address effect modifiers? (e.g. collection of data on known effect modifiers, subgroup analyses, anticipated direction of effect)		$\boxtimes$	
(e.g. misclassification of exposure and outcomes, time-related bias)  Comments:  Section 8: Effect measure modification  8.1 Does the protocol address effect modifiers? (e.g. collection of data on known effect modifiers, subgroup analyses, anticipated direction of effect)			9.9.1
Section 8: Effect measure modification  8.1 Does the protocol address effect modifiers? (e.g. collection of data on known effect modifiers, subgroup analyses, anticipated direction of effect)			9.9.1
8.1 Does the protocol address effect modifiers? (e.g. collection of data on known effect modifiers, subgroup analyses, anticipated direction of effect)			
8.1 Does the protocol address effect modifiers? (e.g. collection of data on known effect modifiers, subgroup analyses, anticipated direction of effect)			
of data on known effect modifiers, subgroup analyses, anticipated direction of effect)	N/A		Section Number
Comments:	$\boxtimes$	$\boxtimes$	

Copyright © 2018 IQVIA. All rights reserved. The contents of this document are confidential and proprietary to IQVIA Holdings Inc. and its subsidiaries. Unauthorized use, disclosure or reproduction is strictly prohibited.

Template No.: RWI\_TP\_EPI0016 Revision 1

Impact of EU label changes on methotrexate for weekly administration

Version 2.0 dated 21 February 2022

Protocol/Study No: SC02 EMA/2018/19/PE

Page 67 of 92

Section	Section 9: Data sources			N/A	Section Number
9.1	Does the protocol describe the data source(s) used in the study for the ascertainment of:				
	9.1.1 Exposure? (e.g. pharmacy dispensing, general practice prescribing, claims data, self-report, face-to-face interview)			$\boxtimes$	
	9.1.2 Outcomes? (e.g. clinical records, laboratory markers or values, claims data, self-report, patient interview including scales and questionnaires, vital statistics)				9.4
	9.1.3 Covariates and other characteristics?			$\boxtimes$	
9.2	Does the protocol describe the information available from the data source(s) on:				
	9.2.1 Exposure? (e.g. date of dispensing, drug quantity, dose, number of days of supply prescription, daily dosage, prescriber)			$\boxtimes$	
	9.2.2 Outcomes? (e.g. date of occurrence, multiple event, severity measures related to event)			$\boxtimes$	
	9.2.3 Covariates and other characteristics? (e.g. age, sex, clinical and drug use history, co-morbidity, co-medications, lifestyle)				
9.3	Is a coding system described for:				
	9.3.1 Exposure? (e.g. WHO Drug Dictionary, Anatomical Therapeutic Chemical (ATC) Classification System)			$\boxtimes$	
	9.3.2 Outcomes? (e.g. International Classification of Diseases (ICD), Medical Dictionary for Regulatory Activities (MedDRA))			$\boxtimes$	
	9.3.3 Covariates and other characteristics?			$\boxtimes$	
9.4	Is a linkage method between data sources described? (e.g. based on a unique identifier or other)			$\boxtimes$	
Comm	ents:				
Section	on 10: Analysis plan	Yes	No	N/A	Section number
10.1	Are the statistical methods and the reason for their choice described?	$\boxtimes$			9.7
10.2	Is study size and/or statistical precision estimated?	$\boxtimes$			9.5
10.3	Are descriptive analyses included?	$\boxtimes$			9.7
10.4	Are stratified analyses included?			$\boxtimes$	
10.5	Does the plan describe methods for analytic control of confounding?			$\boxtimes$	
10.6	Does the plan describe methods for analytic control of outcome misclassification?			$\boxtimes$	

Template No.: RWI\_TP\_EPI0016 Revision 1 Reference: RWI\_WI\_EPI0005

Impact of EU label changes on methotrexate for weekly administration

Version 2.0 dated 21 February 2022

Protocol/Study No: SC02 EMA/2018/19/PE

					Page 68 of 92
Section	on 10: Analysis plan	Yes	No	N/A	Section number
10.7	Does the plan describe methods for handling missing data?				9.7.4
10.8	Are relevant sensitivity analyses described?				
Comme	ents:				
Section	on 11: Data management and quality control	Yes	No	N/A	Section number
11.1	Does the protocol provide information on data storage? (e.g. software and IT environment, database maintenance and anti-fraud protection, archiving)				9.6
11.2	Are methods of quality assurance described?	$\boxtimes$			9.8
11.3	Is there a system in place for independent review of study results?				9.8.2
Comme	ents:				
Section 12: Limitations			No	N/A	Section Number
12.1	Does the protocol discuss the impact on the study results of:				
	12.1.1 Selection bias?	$\boxtimes$			9.9.1
	12.1.2 Information bias?	$\boxtimes$			9.9.1
	12.1.3 Residual/unmeasured confounding? (e.g. anticipated direction and magnitude of such biases, validation sub-study, use of validation and external data, analytical methods).			$\boxtimes$	
12.2	Does the protocol discuss study feasibility? (e.g. study size, anticipated exposure uptake, duration of follow-up in a cohort study, patient recruitment, precision of the estimates)	$\boxtimes$			9.5
Comme	ents:				
Section 13: Ethical/data protection issues			No	N/A	Section number
13.1	Have requirements of Ethics Committee/Institutional Review Board been described?	$\boxtimes$			10.3
Template No.: RWI_TP_EPI0016 Revision 1			Refere	nce: RWI	_WI_EPI0005

Impact of EU label changes on methotrexate for weekly administration

Version 2.0 dated 21 February 2022

Protocol/Study No: SC02 EMA/2018/19/PE

						Page 69 of 92
Section	on 13: Ethical/data protection issues		Yes	No	N/A	Section number
13.2	Has any outcome of an ethical review proaddressed?	cedure been				10.3
13.3	Have data protection requirements been d	lescribed?				10.2
Commo	ents:					
Section 14: Amendments and deviations			Yes	No	N/A	Section number
14.1	Does the protocol include a section to documendments and deviations?	cument				5
Comme	ents:					
G43	15. Diagram 6		\$ 7	NT.	DT/A	G4 
Secu	Section 15: Plans for communication of study results		Yes	No	N/A	Section number
15.1	Are plans described for communicating study results (e.g. to regulatory authorities)?		$\boxtimes$			12
15.2	Are plans described for disseminating study results externally, including publication?					12
Comme	ents:					
Name	e of the main author of the protocol:	[name]				
Date:		17 December				
Signa	ture:					

Template No.: RWI\_TP\_EPI0016 Revision 1 Reference: RWI\_WI\_EPI0005

Protocol/Study No: SC02 EMA/2018/19/PE

Page 70 of 92

# **ANNEX 5. ASSESSMENT OF SUCCESS**

# 5.1 Assessment of Success (Prescriber questionnaire)

Objectives	Questions	Is the question included in the assessment of success? (Yes/No)	Definition of correctly answered question	Assessment of success
	Q1. Please select the option that best describes your experience with the [Direct Healthcare Professional Communication (DHPC): country-specific name] distributed on [country-specific date of distribution] for methotrexate formulations?	Yes	Question completed correctly [Answer '1' or '2' is desirable]	A prescriber is successful for receipt and awareness when he/she receives the DHPC, the HCP guide, the HCP checklist (desirable answers) and is aware of the patient card (desirable answers).  Success for receipt and awareness if ≥80% of prescribers are successful
Receipt and Awareness (5 questions)	Q2. Please select the option that best describes your experience with the [HCP guide: country-specific name] distributed on [country-specific date of distribution]?	Yes	Question completed correctly [Answer '1' or '2' is desirable]	
	Q3. Please select the option that best describes your experience with the [HCP checklist: country-specific name] distributed on [country-specific date of distribution]?	Yes	Question completed correctly [Answer '1' or '2' is desirable]	
	Q4. Please select the option that best describes your experience with the [patient card: name in the local language] (for oral methotrexate formulations)?	Yes	Question completed correctly [Answer '1' or '2' or '3' is desirable]	

Template No.: RWI\_TP\_EPI0016 Revision 1 Reference: RWI\_WI\_EPI0005

Effective Date: 15Jun2018

Page 85 of 92

Objectives	Questions	Is the question included in the assessment of success? (Yes/No)	Definition of correctly answered question	Assessment of success
	Q5. In your daily practice, what version of the educational materials (EM) related to methotrexate do you use?	No; complementary information on mode of distribution		
Knowledge (1 question)	Q6. According to your knowledge about the conditions of use for methotrexate, please indicate if you agree or disagree with the following statements.	Yes	Question completed correctly (16 sub-questions [10 False and 6 True])	A prescriber is successful for knowledge when he/she scores at least 13 out of 16 points (80%) for sub-questions that are correctly answered.  Success for knowledge if ≥ 80% of prescribers are successful.
	Q7. What helps you make treatment decisions while managing patients who have been prescribed, oral and parenteral, once-weekly methotrexate?	No; complementray information on making treatment decisions		A prescriber is successful for self-declared behaviour when all questions regarding self-declared
Self-declared behaviour (7 questions)	Q8. How would you describe your experience with the [HCP guide: country-specific name]?	No; complementary information on user friendliness of educational material		behaviour are completed with desirable answers. Success for self-declared behaviou if $\geq 80\%$ of prescribers are
	Q9. How would you describe your experience with the [HCP checklist: country-specific name]?	No; complementary information on user		successful.

Template No.: RWI\_TP\_EPI0016 Revision 1 Reference: RWI\_WI\_EPI0005

Effective Date: 15Jun2018

Page 86 of 92

Objectives	Questions	Is the question included in the assessment of success? (Yes/No)	Definition of correctly answered question	Assessment of success
		friendliness of educational material		
	Q10. How often do you provide dosing instructions and information about overdose symptoms for once-weekly, oral and parenteral, methotrexate to the patient/caregiver?	Yes	Question completed correctly [Answer '1' is desirable]	
	Q11. Please specify the reasons you choose to not inform the patient/caregiver about the dosing instructions and symptoms of overdose at each/any visit?	No; complementary information on reason for self-declared behaviour to Q10		
	Q12. How do you write down the day of the week the patient should take the once weekly dose of methotrexate, oral and parenteral, in the prescription?	Yes	Question completed correctly [Answer '1' is desirable]	
	Q13. Please specify the reasons you do not write the day of intake in the prescription at each/any visit?	No; complementary information on reason for self-declared behaviour to Q12		

Template No.: RWI\_TP\_EPI0016 Revision 1 Reference: RWI\_WI\_EPI0005

Effective Date: 15Jun2018

Protocol/Study No: SC02 EMA/2018/19/PE Page 87 of 92

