# Table 1 Educational Materials' and Labels' Approval and Dissemination dates

RMM	France	Germany	Greece	Poland*	Sweden
Updated SmPC with boxed warning					
Approved date	04 Nov 2020	11 Nov 2020	10 Jun 2021	-	23 Mar 2020
Distributed date	6 months after approval	6 months after approval	6 months after approval	11 Sep 2020	6 months after approval
Updated PIL with boxed warning					
Approved date	04 Nov 2020	11 Nov 2020	10 Jun 2021	-	23 Mar 2020
Distributed date	6 months after approval	6 months after approval	6 months after approval	11 Sep 2020	6 months after approval
Visual reminder inner packaging					
Approved date	04 Nov 2020	11 Nov 2020	10 Jun 2021	-	23 Mar 2020
Distributed date	6 months after approval	6 months after approval	6 months after approval	11 Sep 2020	6 months after approval
Visual reminder outer packaging					
Approved date	04 Nov 2020	11 Nov 2020	10 Jun 2021	-	23 Mar 2020
Distributed date	6 months after approval	6 months after approval	6 months after approval	11 Sep 2020	6 months after approval
Patient card with space for weekday	·				

Template No.: RWI\_TP\_EPI0016 Revision 1 Reference: RWI\_WI\_EPI0005

Effective Date: 15Jun2018

Copyright © 2018 IQVIA. All rights reserved. The contents of this document are confidential and proprietary to IQVIA Holdings Inc. and its subsidiaries. Unauthorized use, disclosure or reproduction is strictly prohibited.

Protocol/Study No: SC02 EMA/2018/19/PE

Page 22 of 92

RMM	France	Germany	Greece	Poland*	Sweden
Approved date	-	-	-	24 Mar 2020	22 Jan 2020
Distributed date	16 Dec 2020	25 Nov 2019	Soon to be completed	6 months after approval	6 months after approval
HCP checklist					
Approved date	Not Applicable	-	Not Applicable	10 Jun 2020	22 Jan 2020
Distributed date	Not Applicable	18 Mar 2020	Not Applicable	1 month after approval	6 months after approval
HCP guide					
Approved date	18 Mar 2021	Not Applicable	May 2020	10 Jun 2020	22 Jan 2020
Distributed date	6 months after approval	Not Applicable	July 2020	1 month after approval	6 months after approval
DHCP					
Approved date	-	-	17 Sep 2019	18 Dec 2019	23 Sep 2019
Distributed date	09 Apr 2020	25 Nov 2019	27 Nov 2019	6 months after approval	6 months after approval

\*Dates of submission for regulatory approval

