#### Notes:

1. In Poland, the HCP guide and HCP checklist are present in one document.

2. In countries with available information, the date of distribution will be considered, otherwise we will consider 6 months from the date of approval of the EMs. The approval and distribution dates might be varied for different MAHs in one country; therefore, we have referred to the latest date for the approval and distribution per country in this table.

Template No.: RWI\_TP\_EPI0016 Revision 1 Reference: RWI\_WI\_EPI0005

Effective Date: 15Jun2018

Copyright © 2018 IQVIA. All rights reserved. The contents of this document are confidential and proprietary to IQVIA Holdings Inc. and its subsidiaries. Unauthorized use, disclosure or reproduction is strictly prohibited.

Impact of EU label changes on methotrexate for weekly administration

Version 2.0 dated 21 February 2022

Protocol/Study No: SC02 EMA/2018/19/PE Page **23** of **92** 

As a result of these data the following measures were introduced for all oral and parenteral MTX formulations with at least one indication requiring once-weekly dosing (e.g. rheumatologic/dermatological diseases or Crohn's disease):

- Update of summary of product characteristics (SmPC) section 4.2:
  - Only physicians with expertise in the use of MTX and understanding of the risks related to MTX therapy should prescribe MTX;
  - The recommendation to divide the dose has been removed (also package leaflet section 3);
  - Boxed warning that the product must only be taken/used once-weekly (also package leaflet section 3);
  - o Prescribers should ensure that patients or their caregivers will be able to comply with the once-weekly regimen (for oral MTX products only).
- Visual reminder on the outer packaging to take/use the product only once a week
  with space to mark a weekday for intake/use; for MTX-containing products with at
  least one indication requiring treatment once a week and an oncologic indication the
  visual reminder must also include the once-weekly indication
- Visual reminder on the inner packaging that the product must only be taken/used
  once-weekly; for MTX-containing products with at least one indication requiring
  treatment once a week and an oncologic indication the visual reminder must also
  include the once-weekly indication
- Switch from bottle to blister packaging (only oral MTX formulations and over a transition period of 4 years)

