## Assessment of success

In each of the 3 surveys, the proportion of correct or desirable responses across all questions related to the evaluation of the objectives of the surveys will be considered to assess the success.

Template No.: RWI\_TP\_EPI0016 Revision 1 Reference: RWI\_WI\_EPI0005

Protocol/Study No: SC02 EMA/2018/19/PE

Page 46 of 92

The questions considered as complementary will not be included in the assessment of success. The details of the assessment of the success for each survey and each objective is described in Annex 5.

Success at the prescriber, pharmacist, patient level will be defined for each objective based on the number of sub-questions related to that objective being answered correctly or desirably. It is proposed to set the threshold to at least 80% of knowledge questions, including sub-questions, are completed with correct/desirable answers. .

A threshold of 80% successful prescribers/pharmacists/patients on each of the outcomes of awareness, knowledge and self-declared behaviour (self-declared behaviour is not for patients) would be considered appropriate for assessing the effectiveness of RMM.

If additional information from published literature becomes available at the time of reporting, then the results will be discussed in the context of this new information. The methods of reporting and analysis of results obtained will be done as already described in the Protocol and will be further detailed in the SAP.

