## 9.7.4 Handling of Missing Data

The web questionnaire will be programmed in such a way that participants cannot skip questions. We thus do not expect missing values in submitted questionnaires, and neither replacement nor imputation of missing data is expected to be required. Since there is no applicable method unanimously accepted, there will be no replacement or imputation of missing data.

However, on the rare occasion that a system bug may occur and lead to a missing answer in a crucial screener question or a question that is part of the assessment of success, and it is

Template No.: RWI\_TP\_EPI0016 Revision 1 Reference: RWI\_WI\_EPI0005

Protocol/Study No: SC02 EMA/2018/19/PE

Page 47 of 92

not possible to obtain the missing answer through the quality control process as outlined in Section 9.8, the whole questionnaire will be dropped.

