		• German Society for Geriatrics (Deutsche Gesellschaft für Geriatrie e.V.)
		German Society for Internal Medicine (Deutsche Gesellschaft für Innere Medizin e.V.)
		German Society for Child and Adolescent Medicine (Deutsche Gesellschaft)
		für Kinder- und Jugendmedizin)
		The educational material(s) and DHPC were sent to the following:
		Rheumatologists
		Dermatologists
	France	General practitioners
		Oncologists
		
 
Internists
 

2		Emergency physicians
-		Dispensary pharmacists
		Hospital pharmacists
		Private nurses
		Directors of Care
		
 
Nursing staff
 

		
 
Directors of Establishments for Dependent elderly People (EHPAD)
 

		The educational material(s) and DHPC were sent to the following:
		Rheumatologists
		Dermatologists
		Paediatricians
3	Greece	Gastroenterologists
	Greece	Haematologists
		General Practitioners
		
 
Internists and pharmacists of both private and hospital sectors and relevant
 

		scientific societies
		The educational material(s) and DHPC were sent to the following:
1		Oncologists
1		Haematologists
1.		Rheumatologists
4	Poland	General Practitioners
1		• Internists
1		
 
National and provincial consultants of the different specialisations i.e.
 

		oncological, haematological, rheumatological, of internal medicine

Template No.: RWI\_TP\_EPI0016 Revision 1 Reference: RWI\_WI\_EPI0005

Impact of EU label changes on methotrexate for weekly administration Version 2.0 dated 21 February 2022

Protocol/Study No: SC02 EMA/2018/19/PE

Page 62 of 92

5	Sweden	The educational material(s) was sent to the following:
)	Sweden	Rheumatologists
		Dermatologists
		Haematologists
		Paediatrician
		Hospital pharmacists, including head of departments for the specified
		clinics and also Head of department at medicine clinics at the hospitals
		The DHPC was sent to the following:
		Rheumatologists
		Dermatologists
		Gastroenterologists
		Paediatric rheumatologists and chief physician/Head of paediatric clinics and chief physician/Head of medicine clinics

Template No.: RWI\_TP\_EPI0016 Revision 1 Reference: RWI\_WI\_EPI0005

Impact of EU label changes on methotrexate for weekly administration

Version 2.0 dated 21 February 2022

Protocol/Study No: SC02 EMA/2018/19/PE

Page 63 of 92

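### Annex 5.1 requires both the HCP guide and the HCP checklist for prescriber success, but in France, Germany and Greece only one of the two exists, so the rule as written caps success at 40% against an 80% criterion

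*Protocol*

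**What the plan says.** The protocol's Assessment of success text (section 9.7.2.2) refers to Annex 5 for the details and sets the bar: "A threshold of 80% successful prescribers/pharmacists/patients on each of the outcomes of awareness, knowledge and self-declared behaviour" is to be used to judge whether the risk-minimisation measures worked.

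Annex 5.1 marks four prescriber items as counting towards success: Q1 (DHPC), Q2 (HCP guide), Q3 (HCP checklist) and Q4 (patient card). The individual rule is "A prescriber is successful for receipt and awareness when he/she receives the DHPC, the HCP guide, the HCP checklist (desirable answers", followed by awareness of the patient card. The survey-level rule is "Success for receipt and awareness if ≥80% of prescribers are successful". Neither rule says *or*, and neither has a where-applicable clause.

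Table 1 (section 7.2) lists countries in the order France, Germany, Greece, Poland, Sweden. Its checklist row reads "Distributed date Not Applicable 18 Mar 2020 Not Applicable 1 month after approval 6 months after approval". Its guide row is Not Applicable in Germany and carries dates in the other four countries. A note adds: "In Poland, the HCP guide and HCP checklist are present in one document".

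Objective 1.4 (section 8), the variable list (section 9.3.2.1) and the description of the measures (section 7.2) all treat the educational material for healthcare professionals as a checklist *or* a guide.

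**The concern.** The objective asks about one document or the other; the scoring rule asks for both. Three of the five countries have only one. A prescriber there who received everything that was distributed still fails the rule as written.

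The composite would then report that the measures missed the 80% bar because of how success is defined, not because of what reached prescribers. By-country composites for France, Germany and Greece would be 0% by construction and would say nothing about dissemination there. Because the protocol sends the details of success to Annex 5, a later derivation that scored this sensibly would have to depart from the protocol.

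**Working it through.** **The plan's own figure.** Section 9.5.1 gives n = P(1−P)z²/e². With P = 0.5, z = 1.96 and e = 0.08: 0.25 × 3.8416 / 0.0064 = 150.06, which matches the stated 150. The 80% criterion therefore means 0.80 × 150 = 120 successful prescribers.

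**Which countries can satisfy the rule (Table 1).**

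| Country | DHPC | Guide | Checklist | Can meet all |
|---|---|---|---|---|
| France | yes | yes | Not Applicable | no |
| Germany | yes | Not Applicable | yes | no |
| Greece | yes | yes | Not Applicable | no |
| Poland | yes | yes (combined) | yes (combined) | yes |
| Sweden | yes | yes | yes | yes |

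**Unweighted ceiling.** Table 4 indicates 30 prescribers per country. Poland + Sweden = 30 + 30 = 60, and 60/150 = 40.0%. A normal-approximation 95% interval at that ceiling is 0.40 ± 1.96 × √(0.40 × 0.60/150) = 0.40 ± 0.078, or 32.2% to 47.8%.

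**Weighted ceiling.** Section 9.5.3 weights by the real country proportions of prescribers, which the protocol does not give. The ceiling equals the combined weight of Poland and Sweden. With Table 2 sales shares as an assumed proxy, the five-country total is 11.2 + 10.9 + 5.4 + 10.6 + 7.0 = 45.1, and (10.6 + 7.0)/45.1 = 39.0%. A weighted 80% would need Poland and Sweden to hold at least 80% of the prescriber population.

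**Booster recruitment (section 9.2.4.4).** Unweighted, 80% would need at least 120 of 150 completers from Poland and Sweden, all successful. Boosting does not change a population-weighted ceiling.

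**If Q2 or Q3 is skipped where it does not apply.** Three scorings are open:
- Scored as failure: ceiling 60/150 = 40%.
- Removed as unanswered, by extending the denominator rule in section 9.7.1: 60 prescribers remain, none from France, Germany or Greece.
- Scored on the remaining items: ceiling 150/150 = 100%.

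**Illustration of the effect on the verdict.** Assume each distributed item is met independently with probability q, with four items in Poland and Sweden and three elsewhere. The literal rule gives 0.4q⁴; the as-distributed rule gives 0.4q⁴ + 0.6q³.

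| q (assumed) | Literal rule | As distributed |
|---|---|---|
| 0.90 | 26.2% | 70.0% |
| 0.95 | 32.6% | 84.0% |
| 0.98 | 36.9% | 93.4% |

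At q = 0.95 or 0.98 the verdict reverses. At 0.90 both rules fail, but by very different margins.

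**The case against.** The best defence is that the item is never asked where it does not apply. Q2 and Q3 carry placeholders for a country-specific name and distribution date, which a country without the document cannot fill. Sections 9.6.1 and 9.8.1 provide for skip patterns, section 9.9.1 puts country distribution information into the questionnaires, and objective 1.4 suggests an as-applicable intent. The questionnaires are stand-alone documents and are not shown. This stands to the extent that the 40% ceiling belongs to the literal reading only. It does not remove the problem, because nothing in the protocol says how a prescriber with a skipped item is scored.

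A reader might infer several stronger points that the documents do not support:

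- **Questionnaires from the three countries would be dropped under section 9.7.4.** That rule covers "a missing answer in a crucial screener question or a question that is part of the assessment of success", but only where a system bug caused the loss and quality control cannot recover the answer. A programmed country skip is not a bug.
- **Objective 1.1 is bound to fail.** It concerns the DHPC alone, and section 9.7.2.2 reports correct answers question by question, so DHPC receipt is still estimated.
- **Poland's combined document is harmful because it is scored twice.** Under an all-required rule, receiving that document can satisfy both items, so success does not change.
- **Swedish specialty lists lower the ceiling further.** In Annex 2, gastroenterologists appear in the Swedish list under "The DHPC was sent to the following" but not in the one for educational material, and haematologists the reverse. Both lists also include heads of medicine clinics, and no figure can be derived.

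**Conclusion.** The point holds in this form: Annex 5.1 contradicts Table 1 and objective 1.4. Followed literally, it caps the prescriber receipt-and-awareness composite at 40% unweighted (about 39% under assumed sales-share weights), half the 80% criterion, with 0% in France, Germany and Greece. If skip logic applies, the result is undefined rather than capped.

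The figures assume truthful answers (a prescriber who wrongly reports receiving an undistributed document would count as a success), the indicative 30 per country, and full distribution in Poland and Sweden. The 39% also assumes that sales shares stand in for prescriber proportions.

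It would go too far to say that the 80% target can never be reached: Poland or Sweden taken alone could reach it, and scoring on the remaining items would make it attainable overall. What is compromised is the composite verdict, not the per-question estimates.

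**What to change.** Reword the success cell in Annex 5.1 so that a prescriber succeeds with a desirable answer on each of:

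- the DHPC;
- the guide and/or checklist as distributed in the respondent's country: guide in France and Greece, checklist in Germany, the combined document in Poland, both in Sweden;
- awareness of the patient card. Table 1 lists the Greek card's distribution as still to be completed, so score this item in Greece only if distribution is confirmed before fieldwork.

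Add one sentence: an item not distributed in a country is left out of that country's definition, and the respondent stays in the denominator. Carry the same wording into the derivation of the endpoint.

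This raises the structural ceiling from 60/150 to 150/150, so 120/150 becomes attainable. The cost is a rewording of the annex and the matching derivation; no additional data or sample is needed.
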